## **6.8 Study Visit 8 (Week 8 = Day 56±2days) - Treatment Period**

Subjects are not to take their morning dose of study drug at home as pre-dose assessments are conducted at this visit.

- 1 Brief physical examination pre-dose (performed by a physician, nurse practitioner, physician's assistant or nurse). This includes weight and vital signs as well as HEENT, heart, lungs, abdomen and lower extremity.
- 2 Vital signs pre-dose

- 3 Concomitant medications will be recorded
- 4 Adverse events will be recorded
- 5 Laboratory studies (Pre-Dose) (non-fasting):
  - k. Serum chemistry panel, including liver function tests and albumin
  - l. Complete blood count (CBC with differential and platelet count)
  - m. Quantitative PCR for HDV viral load
  - n. Pre-dose blood samples (plasma and serum) for viral mutation analysis, resistance phenotyping, and analysis of drug mechanism and treatment response
  - o. Urinalysis
  - p. Blood sample for monitoring immunologic changes in peripheral blood mononuclear cells (PBMC).
- 6 Dosing Instructions:

Dosing with EBP-994 EBP-994 alone or in combination with Norvir® and/or Pegasys® should occur after the pre-dose vital signs have been taken, the physical examination performed, and pre-dose lab samples drawn. The subject should receive morning dose of study drug(s). If there is not sufficient drug remaining the subject may take the capsules from the container dispensed at this study visit. EBP-994 alone or in combination with Norvir® should be taken orally with 240 mL of water.

The container(s) of study drug(s) along with any unused drug dispensed at Study Visit 6 should be returned at this visit. Study personnel will perform drug accountability on the returned container(s) of study drug(s) to assess dosing compliance. A new container of drug will be dispensed at this visit as well as the diary at the next study visit. At each subsequent Study Visit, drug accountability will be performed for each subject to ensure that subject is compliant with dosing. Subjects should be instructed NOT to take their morning dose of study drug on the morning of the next Study Visit, Day 84, as pre-dose assessments will be conducted. Subjects should be sent home 3 hours post-dose.

If this is the last treatment visit, no new containers of drug(s) will be dispensed and all unused study medication will be collected.

## **6.9 *Study Visit 9-18 (Week 12-48) - Treatment Period***

Subjects are not to take their morning dose of study drug at home as pre-dose assessments are conducted at this visit.

7 Brief physical examination pre-dose (performed by a physician, nurse practitioner, physician's assistant or nurse). This includes weight and vital signs as well as HEENT, heart, lungs, abdomen and lower extremity.

8 Vital signs pre-dose

9 Concomitant medications will be recorded

10 Adverse events will be recorded

11 Laboratory studies (Pre-Dose) (non-fasting):

- p. Serum chemistry panel, including liver function tests and albumin
- q. Complete blood count (CBC with differential and platelet count)
- r. Quantitative PCR for HDV viral load
- s. Pre-dose blood samples (plasma and serum) for viral mutation analysis, resistance phenotyping, and analysis of drug mechanism and treatment response
- t. Urinalysis
- u. Blood sample for monitoring immunologic changes in peripheral blood mononuclear cells (PBMC).

12 Dosing Instructions:

Dosing with EBP-994 EBP-994 alone or in combination with Norvir® and/or Pegasys® should occur after the pre-dose vital signs have been taken, the physical examination performed, and pre-dose lab samples drawn. The subject should receive morning dose of study drug. If there is not sufficient drug remaining the subject may take the capsules from the container dispensed at this study visit. EBP-994 and/or Norvir® should be taken orally with 240 mL of water.

The container(s) of study drug(s) along with any unused drug dispensed at Study Visit 7 should be returned at this visit. Study personnel will perform drug accountability on the returned container(s) of study drug(s) to assess dosing compliance. A new container of drug will be dispensed at this visit to the subject. Subjects should be instructed to return all container(s) and any unused study medication at the next study visit. At each subsequent Study Visit, drug accountability will be performed for each subject to ensure that subject is compliant with dosing. Subjects should be instructed NOT to take their morning dose of study drug on the morning of the next Study Visit, Day 112, as pre-dose assessments will be conducted. Subjects should be sent home 3 hours post-dose.

If this is the last treatment visit, no new containers of drug(s) will be dispensed and all unused study medication will be collected.

## **6.10 Study Visit 19 – Four Week Post-Treatment Follow-Up**

Same assessments are taken as in 6.9. No new containers of drug(s) will be dispensed. All unused study medication will be collected. No dosing at this visit.

## **6.11 Supplemental Safety Evaluation Visit(s)**

During the course of the study, if the Investigator has a specific safety concern that may merit additional safety evaluation(s), the Medical Monitor should be notified of the intent to perform additional Study Visit(s) and/or additional laboratory assessments(s). These visits will be considered Unscheduled Visits.

# **7 ASSESSMENT OF SAFETY**

## **7.1 Procedures For Recording Adverse Events**

All adverse events encountered during the clinical study will be recorded on the case report form (CRF). An adverse event is defined by the International Conference on Harmonization (ICH) as follows:

- Any untoward medical occurrence in a patient or clinical investigation subject administered a pharmaceutical product and which does not necessarily have a causal relationship to this treatment
- An adverse event (AE) can therefore be any unfavorable and unintended sign (including any abnormal laboratory finding for example), symptom, or disease temporarily associated with the use of a experimental drug, whether or not considered related to the experimental drug

An adverse event is any adverse change from the subject's baseline condition, including any clinical or clinically significant laboratory test value abnormality that occurs during the course of the clinical study after the experimental drug has been utilized, whether the adverse event is considered related to the treatment or not.

All adverse events will be followed until resolution. This may require obtaining clinical blood samples for appropriate laboratory tests until their values return to baseline levels or performing follow-up physical examinations until resolution of identified abnormalities.

### **7.1.1 Routine Reporting of Adverse Events**

Adverse events, whether or not associated with study drug administration, will be recorded on the Adverse Event Reporting form of the CRF and will be submitted to the sponsor at regularly scheduled intervals.

The information to be entered in the CRF will include:

1. The time of onset of any new adverse event or the worsening of a previously observed adverse event
2. The specific type of reaction in standard medical terminology
3. The duration of the adverse event (start and stop dates)
4. The severity/grade of the adverse event
5. An assessment should be made of the relationship of the adverse event to the study drug, i.e., according to the definitions in Section 7.1.4.
6. Description of action taken in treating the adverse event and/or change in study drug administration or dose

Follow-up assessments should be repeated to document return of any abnormalities to normal, or to document other outcome of the adverse event.

### **7.1.2 Reporting of Serious Adverse Drug Experiences, including Deaths**

A serious adverse drug experience (SAE), as defined by the International Conference on Harmonization and in 21 CFR 312.32 is:

Any adverse drug experience occurring at any dose that results in any of the following outcomes:

1. Death
2. A life threatening adverse drug experience
3. Inpatient hospitalization or prolongation of existing hospitalization
4. A persistent or significant disability/incapacity
5. Congenital anomaly/birth defect

Important medical events that may not result in death, be life-threatening, or require hospitalization may be considered a serious adverse drug experience when, based upon appropriate medical judgment, they may jeopardize the patient or subject and may require medical or surgical intervention to prevent one of the outcomes listed in this definition. Examples of such medical events include allergic bronchospasm requiring intensive treatment in an emergency room or at home, blood dyscrasias or

convulsions that do not result in inpatient hospitalization, or the development of drug dependency or drug abuse.

Serious adverse experiences, including death due to any cause, which occur during this study or within 30 days following the last dose of study medication, whether or not related to the administration of study drug, must be reported immediately (within 24 hours of learning of the event) to the Medical Monitor.

Contact: [name], DPhil  
[contact] Email: [[contact]](mailto:[contact])  
[[contact]](mailto:[contact])

International calls to the United States: dial 00 + 1 before the telephone number

### **7.1.3 Severity of Adverse Drug Experiences**

Clinical adverse events will be categorized using the following definitions:

**Mild:** discomfort noted, but no disruption of normal daily activity

**Moderate:** discomfort noted of sufficient severity to reduce or adversely affect normal activity

**Severe:** incapacitating, with inability to work or perform normal daily activity

### **7.1.4 Relationship of Adverse Events to the Study Drug**

The investigator and/or Medical Monitor should record on the CRF whether the event is best described as unrelated, possibly, probably, or definitely related association to the study medications, according to the following definitions.

**Unrelated:** There is evidence that the adverse event definitely has an etiology other than the assigned study drug.

**Possibly Related:** The adverse event has a temporal relationship to study drug administration. However, an alternative etiology may be responsible for the adverse event. Information on drug/product withdrawal may be lacking or unclear.

**Probably Related:** The adverse event has a temporal relationship to study drug administration. The event is unlikely to be related to an alternative etiology. There is a reasonable response on withdrawal (dechallenge). Rechallenge information is not required.

**Related:** The adverse event has a temporal relationship to study drug administration and resolves when the drug is discontinued. An alternative etiology is not apparent. If the subject is rechallenged with the assigned study drug, the adverse event recurs. Rechallenge is not necessarily required.

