### **Safety**

Safety will be monitored by assessing vital signs, adverse events, concomitant medications and laboratory and ECG results. ECGs will be conducted in triplicate and vital signs assessed at each Study Visit.

The most common side effects seen with lonafarnib (the active ingredient of EBP-994) are gastrointestinal (diarrhea, nausea, and vomiting). There were no serious adverse events (SAEs) observed in the studies conducted in healthy volunteers. The SAEs reported in at least 2% of subjects in the Phase 1 and Phase 2 studies conducted in subjects with solid tumors or hematologic malignancies included fever (6%), diarrhea (6%), dehydration (6%), febrile neutropenia (4%) and sepsis (4%).

As with any anti-viral medication, a possible effect of EBP-994 is viral resistance. Hepatitis D viral load levels will be measured through quantitative PCR at all Study Visits. Viral mutation analysis and resistance phenotyping will be conducted to assess viral resistance to the study medication. The investigator may terminate the subject from the trial if, in his/her opinion, there is an unacceptable increase in HDV viral load. Moreover, the investigator is free to initiate standard of care (SOC) medications and doses (i.e. Pegasys®) at any time point.

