## 3 STUDY DESIGN

This study is a phase II, randomized, open label study of up to 48 weeks of treatment with EBP-994 alone, or in combination with Norvir® and/or Pegasys® in subjects chronically infected with HDV genotype 1. The investigator is free to initiate licensed medications at any time point and decrease the dose of EBP-994 if deemed warranted for GI side effects. The duration of the study for each subject will be approximately 11-55 weeks (up to three week screening period, up to 48 week treatment period and four week safety follow-up period).

The duration of the entire study is anticipated to be approximately 36 months (first subject in to last subject out). Pharmacokinetic sampling will be done at Day 1 and Day 28 of dosing. PK sampling will be conducted only on subjects who have consented to participate in the PK portion of this study. Participation in PK sampling is optional for each subject.

At the Screening Visit, subjects giving written informed consent will have all required evaluations to determine their eligibility to participate in the study. The outpatient screening visit must occur within 21 days of Study Visit 1.

Each eligible subject will undergo 8-16 Study Visits; Screening, Day 1, Day 2, Day 3, Day 7, Day 14, Day 28, then every 4 weeks (total duration depends on assigned treatment group), followed by a Safety Follow-Up Visit, 4 weeks post-treatment. Study drug will consist of EBP-994 alone or in combination with either Norvir® and/or Pegasys®, depending on which group the subject has been randomized to on the Day 1 visit. Moreover, the investigator is free to initiate licensed medications at any time point and decrease the dose of EBP-994 if deemed warranted for GI side effects.

During the intervals between Study Visits, subjects will be free to carry on their usual activities of daily living. Subjects will be instructed to take their study medication at appropriate dosing intervals. Efforts should be made to schedule Study Visits according to the study protocol; however the window for consecutive Study Visits will be  $\pm 2$  days with the exception of Day 2 and Day 3 for which a visit window is not allowed.

Safety will be monitored by assessing vital signs, adverse events, concomitant medications, laboratory and ECG results. ECGs will be conducted and vital signs assessed at each Study Visit.

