### **5 STUDY TREATMENT**

#### **5.1 *EBP-994***

The drug to be utilized for this study is EBP-994 (previously developed as lonafarnib by Schering-Plough, now Merck). The EBP-994 active pharmaceutical ingredient (API) is manufactured by Schering Corporation located in [name]. Each capsule contains 25 mg, 50 mg or 75 mg of EBP-994.

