### **8.4 Safety**

#### **8.4.1 Adverse Events**

All reported adverse events will be mapped to standard coding terms (MedDRA) and grouped by system organ class and preferred terms. The incidence of adverse events will be tabulated by seriousness, severity, and relationship to study drug. If an adverse event is reported more than once during the study period, the greatest severity and worst-case attribution will be presented in tables. Adverse events will also be listed for individual subjects, along with information regarding onset, duration, severity, and relationship to study drug. Adverse events that lead to withdrawal from the study will be listed and summarized by treatment group separately. Summary tables and listings of serious adverse events will also be generated.

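### Adverse-event causality is graded once against an inconsistently defined study drug, so in the three combination groups the planned relatedness table cannot show which events are attributed to EBP-994

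*Combined protocol and SAP*

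**What the plan says.** The combined protocol and SAP describes the object of the causality grade in three ways.

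- Section 3 ties it to the randomized regimen: "Study drug will consist of EBP-994 alone or in combination with either Norvir® and/or Pegasys®, depending on which group" the subject is in.
- Section 5.1 points to one agent: "The drug to be utilized for this study is EBP-994".
- Section 7.1.4 introduces the scale as running up to a "definitely related association to the study medications", in the plural. Its definitions then refer to the assigned study drug in the singular.

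Section 7.1.1, item 5, has the CRF hold one relationship assessment per event, to the study drug. Item 6 records action taken and any dose change, again for study drug with no component named. Section 7.1.4 allows *Unrelated* only where "There is evidence that the adverse event definitely has an etiology other than the assigned study drug". For *Possibly Related* it says: "However, an alternative etiology may be responsible for the adverse event".

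The analysis follows the same grade. Section 8.4.1 states: "The incidence of adverse events will be tabulated by seriousness, severity, and relationship to study drug". Repeated events are collapsed to the worst attribution. Only events leading to withdrawal are said to be summarized by treatment group.

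On treatment outside the assignment, the Safety part of the Protocol Summary says "the investigator is free to initiate standard of care (SOC) medications and doses" at any time, and gives Pegasys as the example.

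**The concern.** The fourth primary objective in Section 2 covers the safety and tolerability of EBP-994 alone and together with Norvir and/or Pegasys. A reader of the safety tables will want to know two things: how the regimen was tolerated, and which events the investigator put down to EBP-994.

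A single grade against a two- or three-drug regimen answers at most the first. If the term is read as EBP-994 only, it answers at most the second. Because the protocol supports both readings, two raters could grade the same event differently and both follow the text.

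The investigator's view of which component was responsible is best recorded when the event occurs. If it is not asked for then, it has to be inferred later from exposure records.

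**Working it through.** The plan states no figure on this point and no formula applies. The check sets the sections side by side.

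**Step 1: how many drugs one grade covers.** The group list is in the Protocol Summary and Section 6.2, and the regimen definition is in Section 3.

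| Group | Assigned drugs | Drugs under one grade |
|---|---|---|
| 1 | EBP-994 | 1 |
| 2 | EBP-994, Norvir | 2 |
| 3 | EBP-994, Pegasys | 2 |
| 4 | EBP-994, Norvir, Pegasys | 3 |

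Three of four groups have more than one drug under the grade. The maximum enrolment is 75 and no allocation ratio is given. Under an assumed equal split, 75 × 3/4 = 56.25, or about 56 subjects. This counts subjects in affected groups, not events wrongly attributed.

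**Step 2: does either reading of study drug solve the problem?**

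- *Regimen (Section 3, and the word assigned in Section 7.1.4).* In Groups 2 to 4 a related event is related to the combination. EBP-994 cannot be isolated in the Section 8.4.1 table.
- *EBP-994 only (Section 5.1; Section 7.3 also describes only lonafarnib effects).* EBP-994 is isolated, but events attributed to Norvir or Pegasys have no causality field, although the combinations are part of the primary objective.

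The regimen reading is better supported. Neither reading gives both answers.

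**Step 3: do the grade definitions work for a regimen?** *Probably Related* relies on response to withdrawal, and *Related* on resolution after discontinuation. Neither says which drug is meant. The Study Design text and Section 7.3 allow EBP-994 alone to be reduced for gastrointestinal effects, so components can be changed separately, and item 6 of Section 7.1.1 does not ask which one was.

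**Step 4: Pegasys added outside the assignment.** Take the regimen reading and an event in a subject receiving Pegasys.

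| Situation | Grade under Section 7.1.4 |
|---|---|
| Group 1 or 2, Pegasys added, event definitely due to Pegasys | *Unrelated* |
| Group 3 or 4, same event | One of the related grades |
| Group 1 or 2, Pegasys added, cause uncertain | *Possibly Related*; the contrast shrinks or disappears |

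Under the EBP-994-only reading the contrast does not arise. So the asymmetry requires three things together: added Pegasys, definite attribution to it, and the regimen reading. The documents give no rate for the first two, so no size can be calculated.

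**Step 5: what else could separate the components?** Group 1 is a randomized monotherapy group, and Appendix A has concomitant medications recorded at every visit. However, the daily dose caps for EBP-994 differ between groups. They also conflict between documents: the Protocol Summary gives up to 600 mg for Group 3 and 150 mg for Group 4, while Section 6.2 gives 200 mg for both. Those passages must be reconciled. A comparison with Group 1 is therefore not a clean measure of what the partner drugs add.

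**The case against.** The strongest reply has four parts.

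*The regimen is the object of study.* Interferon effects in a group assigned interferon are part of that regimen's safety and belong in its table. This stands. A reader might infer that Groups 3 and 4 are made to look worse by definition. The documents do not support that: where Pegasys is assigned, more Pegasys events reflect a real difference in exposure. For the same reason, turning an assumed interferon event rate into a percentage-point gap between groups would mostly measure real toxicity, not an artefact of grading. The remaining problem is that such events could be misread as EBP-994 toxicity.

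*The cross-group asymmetry is not a rule.* This also stands. A reader might infer that any Pegasys event is unrelated in Group 1 and related in Group 3, with a low neutrophil count as the obvious example. But *Unrelated* needs definite evidence of another cause, and Section 7.3 lists febrile neutropenia (4%) among serious events in oncology studies of lonafarnib. *Possibly Related* would be the more natural grade. Adding Pegasys may also need Medical Monitor approval under Section 5.3, if it counts as an immune modulating agent under Section 4.2.

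*The information is not lost.* Partly right. Subject listings, concomitant medications, onset, duration and dose changes are all kept, and every event still appears in the tables by seriousness and severity. The limitation is in the causality field and its table, not in the whole database. But exposure records do not contain the investigator's judgement at the time.

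*The CRF may already have separate fields.* Possible. It is not among the documents, and the protocol does not forbid them. Nor does the protocol require them, and Section 8.4.1 plans no table that would use them.

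**Conclusion.** The point holds in a limited form. The protocol requires one causality grade against a term it defines inconsistently, and asks for none per component. In Groups 2 to 4 the planned relatedness table cannot attribute events to EBP-994 as distinct from Norvir or Pegasys. Reading study drug as EBP-994 only moves the gap to the partner drugs.

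Three of four groups are affected; the figure of about 56 of 75 subjects rests on an assumed equal allocation. No number of misattributed events and no between-group distortion can be derived from the documents. The differing grade for Pegasys added in Group 1 or 2 is a conditional side effect. The conclusion rests on the protocol text, since the CRF was not available.

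This is worth correcting even in a descriptive pilot, because the safety of the combinations is a primary objective and the remedy is cheap.

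**What to change.** 1. Define study drug once, and use the term consistently in Sections 3, 5.1, 7.1.1, 7.1.4 and 8.4.1.
2. In Section 7.1.1, item 5, and Section 7.1.4, record relationship separately for EBP-994, Norvir and Pegasys, for each component the subject is receiving. Include Pegasys added outside the assignment.
3. In Section 8.4.1, tabulate all adverse events per treatment group, by relationship to EBP-994 and by relationship to any component.

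The cost is about two extra causality fields on the adverse-event form and one more table. Treatment does not change. Attribution to a component in a combination group remains a judgement, which is why the any-component table should stand beside the EBP-994 table.

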### **Clinical Safety Summary**

There are currently no HDV-specific therapies. EBP-994 could be the first direct acting anti-HDV agent by disrupting the HDV life cycle through inhibition of prenylation at the level of host cell farnesyl-transferase. EBP-994 has been dosed in human studies examining PK and PD and has exhibited inhibition of farnesyl transferase at levels below the maximally tolerated dose (MTD; 300 mg BID). A risk associated with the use of direct acting antiviral agents would be the development of resistance by the virus. However, because prenylation is a host function not coded for by the HDV genome, the risk of resistance development could be mitigated. Viral surveillance will be conducted throughout the conduct of the study to assess the risk of viral resistance. Two doses of EBP-994 alone, or in combination with Norvir® and/or Pegasys® will be examined in this proof-of-concept study, 200 vs. 300 mg

(PO BID), and the adverse profile will be correlated to the clinical benefit of viral suppression.

Other risks that may be encountered with the treatment of HDV include an increase in liver function tests during and after therapy, the risk of a flare in HBV ( $\geq 1$  log increase in HBV viral load) as the HDV viral load goes down, and an increase in HDV viral load after therapy is ended. Flares in liver function tests are not uncommon with the start of treatment of HBV disease and necessitate a careful and frequent review of liver function studies. We will follow the same approach in this study unless there is a concomitant flare in HBV viral load. A flare of HBV viral load while on EBP-994 will be treated by starting specific anti-HBV therapy using one of the 5 approved drugs, the selection being made by the Investigator based on the subject's condition and history of prior anti-HBV therapy. A flare in HDV viral load after the termination of EBP-994 will be watched closely and interferon therapy may be started as determined by the investigator.

Finally, the known adverse event profile for EBP-994 (and all other prenylation inhibitors in clinic) is primarily gastrointestinal, primarily dose related diarrhea as well as nausea and vomiting.

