### **8.7 Sample Size And Power**

The sample size has not been determined by strict statistical considerations. From a safety, pharmacokinetic and pharmacodynamic perspective, no a-priori assumptions are made as to the expected treatment effect and associated variability.

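### Symptom-free laboratory adverse events have no valid severity grade, and the causality wording keeps events without a positive dechallenge out of the top two relatedness categories

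*Combined protocol and SAP*

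**What the plan says.** Section 7.1 defines an adverse event as an adverse change from baseline, "including any clinical or clinically significant laboratory test value abnormality that occurs during the course of the clinical study" after drug has been used. Section 7.1.1 lists a severity or grade and a relationship assessment among the items recorded for each event.

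Section 7.1.3 gives one severity scale and introduces it as applying to clinical adverse events. Mild is "discomfort noted, but no disruption of normal daily activity". Moderate is discomfort that reduces normal activity. Severe is incapacity. No laboratory grading appears there, in 7.3 or in Section 8.

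Section 7.1.4 has four causality categories:

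- Unrelated needs evidence that the event definitely has another cause.
- Possibly Related needs a temporal relationship. It says another cause may be responsible and that withdrawal information may be lacking or unclear.
- Probably Related needs a temporal relationship, an unlikely alternative cause, and that "There is a reasonable response on withdrawal (dechallenge").
- Related is worded as follows: "The adverse event has a temporal relationship to study drug administration and resolves when the drug is discontinued". It also needs the absence of an apparent alternative cause.

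The Clinical Safety Summary in 1.2 names "an increase in liver function tests during and after therapy" as a risk. It also names an HBV flare, defined there as a rise of at least 1 log in HBV viral load. The preclinical summary reports thrombocytopenia and raised AST in monkeys.

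Section 8.4.1 tabulates event incidence by seriousness, severity and relationship. Section 8.4.2 gives descriptive statistics and listings for laboratory data.

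**The concern.** Safety and tolerability are primary objectives (Section 2), and the planned adverse event tables are split by these two ratings. Several risks that the protocol itself names are detected in the laboratory and may cause no symptoms, and one can begin after the drug is stopped. If the definitions cannot rate such events, the tables will omit them, rate them by default, or depend on how each rater departs from the text. A reader of the severity table could then see little severe toxicity because laboratory toxicity was never gradeable. A reader of the relationship table could see few events in the upper categories because the entry condition could not be met.

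**Working it through.** No arithmetic applies. There is no figure in the plan to reproduce, since Section 8.7 says "The sample size has not been determined by strict statistical considerations" and no event rates are assumed. The check sets each written definition against the kinds of event the protocol anticipates.

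**Severity (7.1.3)**

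| Event | Mild | Moderate | Severe |
|---|---|---|---|
| Symptom-free ALT or AST rise | no: needs discomfort | no: needs discomfort and reduced activity | no: needs incapacity |
| Symptom-free low platelets or neutrophils | no | no | no |
| HBV DNA flare without symptoms | no | no | no |
| Diarrhea, nausea, vomiting | can be met | can be met | can be met |

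The first three rows meet none of the three levels, yet 7.1 makes them adverse events when clinically significant and 7.1.1 asks for a grade. Read strictly, the result is ungraded. Mild would be a default chosen by the rater.

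**Causality (7.1.4)**

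| Event | Probably Related | Related |
|---|---|---|
| Improves off drug but does not resolve | can be met: only a reasonable response is asked | no: resolution is required |
| Drug stopped, no response (fatal events included) | no | no |
| Settles while dosing continues | no: there was no withdrawal | no: the drug was not discontinued |
| Starts after the last dose, such as a post-therapy liver-test flare | no: nothing is left to withdraw | no |

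For the last three rows the ceiling is Possibly Related, the second of four categories. Even that fits imperfectly when no other cause is plausible, because its definition says another cause may be responsible.

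An event with no temporal link and no proven other cause fits nothing. Unrelated needs evidence of a definite other cause, and the other three categories each need a temporal relationship.

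The text says rechallenge need not be done, for both Probably Related and Related. It has no matching waiver for dechallenge, so dechallenge reads as a condition.

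**Whether later sections repair this**

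- 8.4.1 reports the greatest severity and worst-case attribution for repeated events. That selects among ratings already given and cannot supply a missing grade or exceed the ceiling.
- 8.4.2 reports laboratory values but plans no grades or shift tables.
- Post-treatment events will arise for rating. The four-week follow-up visit (6.10) repeats the 6.9 assessments, including adverse events, chemistry and blood count.

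**The case against.** The best counter-argument is that little is lost. SAEs are reported whether or not related (7.1.2), blood dyscrasias are an explicit example of an important medical event there, and 8.4.1 tabulates seriousness separately. Laboratory values are listed by subject (8.4.2), and abnormalities reach the Medical Monitor and the investigator promptly (7.3). The rater is asked which category best describes the event, which leaves judgement. The CRF is not in the documents and could carry a laboratory grade. All of this stands and limits the consequence. It does not supply a grade or remove the dechallenge condition: 7.1.4 ties the judgement to its own definitions, so using discretion means departing from them.

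A reader might also infer more than the text supports:

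- *Any unresolved event is capped at Possibly Related.* It is not; a reasonable response is enough for Probably Related.
- *The definitions place serious laboratory toxicity at mild.* Even mild needs discomfort, so the strict result is no grade.
- *The gastrointestinal profile is misrated.* These events are symptomatic and fit the severity scale. They can show dechallenge if drug is stopped, including at the end of treatment. Only those that settle while dosing continues are affected.
- *HDV rebound after treatment is an example.* Under 7.1 an adverse event is a change from baseline, so a return toward baseline is not clearly one, and it is reported as pharmacodynamic data (8.6).
- *A single rating for combination therapy is part of the defect.* Rating each drug separately is a preference. Drugs started together are hard to separate by opinion, and the monotherapy group offers a contrast, though an incomplete one.

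**Conclusion.** The point holds in a limited form. Symptom-free laboratory adverse events satisfy none of the three severity levels. Three kinds of event (no response off drug, no withdrawal, onset after treatment) cannot meet the written criteria for the top two of four causality categories. One kind (no temporal link, no proven other cause) fits no category.

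These statements follow from the definitions and say nothing about how many events will be affected; the documents give no basis for a count. The effect is on two descriptive splits of the adverse event tables. SAE reporting and laboratory listings are unaffected, and no hypothesis test on adverse events is planned.

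The conclusion assumes that the definitions are applied as written and that no separate laboratory grading exists on the CRF. It also depends on how relationship is displayed. If Possibly Related is pooled with the higher categories, a related-versus-unrelated table changes little; no pooling rule is stated. The change is worth making because the tables serve a primary objective and the repair is cheap.

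**What to change.** 1. **Section 7.1.3.** Keep the three-level scale for clinical events. Grade laboratory adverse events by value, using a named published laboratory toxicity table applied to the chemistry and blood count results already collected. Identify an HBV flare by the 1-log definition in 1.2. State in 8.4.1 that this grade is used in the severity tables.
2. **Section 7.1.4.** For Probably Related and Related, make dechallenge supporting evidence where it is available and applicable, and no longer a requirement. Extend Unrelated to events with no plausible temporal link.

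Recording relationship separately for each drug is optional and not needed to resolve this point.

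The cost is wording in two sections, a matching line in 8.4.1 and some programming. Chemistry and blood count grading needs no new visit or sample. The HBV criterion can be applied only where HBV DNA is measured: the visit lists in 6.2 to 6.9 name HDV PCR only, and the HBV DNA row of Appendix A is incomplete in the text available, so the measurement times should be confirmed. The downside is small: more events may be classed as related or severe.
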